Bacillus Calmette-Guérin (BCG) was developed as a vaccine against tuberculosis, but many studies have shown its ability to induce potent protection against other infectious diseases: the so called non-specific effects (NSEs).[5] Moreover, BCG has non-specific clinical protective effects: early administration of BCG vaccination leads to reduced child mortality, mainly as a result of reduced neonatal sepsis, respiratory infections, and fever.[1, 5] NSEs of BCG are not limited to children, as a recent study in adolescents has shown a 70% decrease in the incidence of respiratory tract infections in individuals vaccinated with BCG compared to placebo.[6] In addition, a small Indonesian trial has shown that consecutive BCG vaccination for 3 months reduced the incidence of acute upper tract respiratory infections by 80% (95%CI=22-95%).[7] The non-specific beneficial effects of BCG are not restricted to infections, as BCG has also been used in patients with bladder cancer, to induce an improved reaction of the immune system, which prevents tumor progression and mortality.[8]

It has been recently demonstrated that the non-specific beneficial effects of BCG vaccination are due to epigenetic and metabolic reprogramming of innate immune cells such as myeloid cells and NK cells, leading to an increased antimicrobial activity, a process termed 'trained immunity'.¹² Upon stimulation with a pathogen, the innate immune system becomes primed and is able to react faster and more efficient to a secondary (and non-related) stimulus. In experimental studies, BCG has been shown to protect not only bacterial and fungal infections, but against viral infections such as influenza as well.[9] Furthermore, among humans receiving yellow fever vaccine virus, those who had received BCG had less viremia, and improved anti-viral responses compared to placebo treated subjects.[10] The observed effects are proposed to be due to modulation of the human innate immune system through 'trained immunity' and are long-lasting for at least one year

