BCG induced non-specific immunity has been linked to chromatin conformation and DNA methylation. Therefore, these additional epigenetic studies will be evaluated as part of secondary analysis. The Illumina Infinium MethylEPIC array tests ~850,000 methylation sites including promoters, enhancers and non-island sites. Briefly, genomic DNA (gDNA) will be isolated (DNeasy protocol) from 1×10^6 PBMCs with >80% viability. From this quantity of PBMCs, I am able to retrieve >1.5 μ g DNA, which is sufficient to implement this assay (500ng). Experiments only proceed after strict quality control analyzing nucleic acid quality using a Qubit 3.0 fluorometer and Agilent 4200 Tape Station System. I will use the Zymo EZ DNA Methylation kit to bisulfite treat 500ng of gDNA prior to MethylEPIC testing. Methylation IDAT files will be imported into R statistical system using the Bioconductor (<http://www.bioconductor.org>) minfi package. After preprocessing and normalization, the Bioconductor limma package will identify probes with greater than 2 or less than 0.5-fold differential methylation with p-values < 0.05. Statistically significant differentially methylated probes will be visualized in Ingenuity Pathway Analysis. Gene ontology (GO) and Gene Set Enrichment Analysis analysis will be implemented using Molecular Signature Database (MSigDB) using hyper-geometric distribution that accounts for multiple comparisons. To evaluate if cell composition is confounding results and to determine the DNA methylation status of specific cell types (CD4, CD14, CD8, NK, and B cells), I will implement the bioinformatic pipelines EDEC (Epigenomic deconvolution) and MeDeCom (methylation decomposition). Both methods utilize linear algebra and classification techniques to quantify the DNA methylation profiles in several steps: 1) identifying optimal number of informative cell subpopulations 2) identify simultaneously both the estimated percentage of and the DNA methylation profile of each cell subpopulation. The explanatory cell subpopulations are then matched to DNA methylation profiles of known references via Spearman correlation. This approach offers multiple benefits: it enables us to assess DNA methylation changes in a cell type specific manner, but in a cost-effective approach because I will be profiling only the heterogeneous blood cells. Validation of bioinformatic EDEC results will then be carried out in magnetic bead purified cell types as described below.

j. ATAC-seq

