DNA hyper-methylation inversely correlates with chromatin accessibility, however other means of epigenetic silencing exists (i.e H3K27me3, etc.). Therefore to confirm that specific DNA hyper-methylation marks correlate with decreased chromatin accessibility, we will implement ATAC-seq, epigenome-wide chromatin accessibility evaluation. 1×10^5 cells of interest (identified after EDEC as described above) undergo cell lysis, Tn5-mediated transposition followed by DNA purification, PCR amplification, DNA quality Bioanalysis (using Agilent and Qubit as described above) and sequencing. Bioconductor packages will be used for preprocessing, normalizing and identification of differential chromatin accessibility defined as greater than 2 or less than 0.5-fold difference with p values < 0.05.

k. Benefits and risks assessment, group relatedness

The risk to and burden for the subject of BCG vaccination is estimated to be low, according to two previous trials that have been performed with BCG vaccines.[7, 11, 13] The beneficial effect BCG vaccination for the individualized participant is unknown, although the objective is to prevent severe illness to SARS-CoV-2 infection. Using an adaptive design, the study aims to find a positive effect of BCG-vaccine on a population level, which could be applied quickly in participants allocated to placebo and implemented to hospitals that do not participate in the study.

11. STRUCTURED RISK ANALYSIS**a. Potential issues of concern**

An extensive description of the mechanisms of action of the BCG vaccine, referring to the available in vitro and in vivo evidence, could be found in the Summary of Product Characteristics and the Product Insert.

a. Level of knowledge about mechanism of action

BCG activates NOD2 receptor pathway, and subsequently induces long-term epigenetic changes in chromatin of myeloid cells.[10, 13] The epigenetic reprogramming leads to increased antimicrobial activity of myeloid cells (cytokine production, phagocytosis, reactive oxygen species release). At the same time, BCG induces potent activation of cellular specific immunity, with strong induction of Th1 responses and IFNg release.

b. Previous exposure of human beings with the test product

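### Section 10.i calls differential methylation by a two-fold rule with no stated scale; in bulk PBMC DNA it would miss most moderate changes confined to a minority of cells

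*Combined protocol and SAP*

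**What the plan says.** Section 10.i describes the assay as follows: "The Illumina Infinium MethylEPIC array tests ~850,000 methylation sites including promoters, enhancers and non-island sites". The DNA comes from PBMCs that are not sorted by cell type; the plan calls this cost-effective "because I will be profiling only the heterogeneous blood cells". After normalization, the "limma package will identify probes with greater than 2 or less than 0.5-fold differential methylation with p-values < 0.05". The probes so called go to pathway analysis. The scale of the fold is not given, and no other criterion for differential methylation appears.

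The same section then plans two deconvolution methods, EDEC and MeDeCom, and says of the approach that "it enables us to assess DNA methylation changes in a cell type specific manner". Validation in purified cells follows. The text does not say whether deconvolution uses all probes or only those that passed the bulk rule, and it sets no threshold for a cell-type difference.

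On where the BCG effect sits, Section 1 speaks of "epigenetic and metabolic reprogramming of innate immune cells such as myeloid cells and NK cells", and Section 11 (mechanism of action) says that BCG "induces long-term epigenetic changes in chromatin of myeloid cells". Section 10.j adds ATAC-seq "to confirm that specific DNA hyper-methylation marks correlate with decreased chromatin accessibility", with the same fold and p-value thresholds.

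**The concern.** Methylation at a probe is a fraction between 0 and 1. A fold threshold suits read counts, as in ATAC-seq, but on a bounded fraction it demands very different absolute changes at different baselines and makes some changes impossible to call. The plan also expects the effect mainly in innate cells but measures a mixture. A change in a minority of cells is diluted in proportion to their share before the threshold is applied.

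At stake is the list of probes that feeds the pathway analysis. If moderate real changes cannot reach the threshold, a short or empty bulk list is hard to interpret. If tiny changes near zero do reach it, the list leans towards probes of little interest.

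**Working it through.** The two-fold limit is a chosen threshold, so there is no derived figure to reproduce. The plan gives no sample size or power for the methylation work.

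**Inputs from the plan:** fold above 2 or below 0.5; p < 0.05; about 850,000 probes; unsorted PBMCs; effect placed in myeloid and NK cells.

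**Assumed, not in the documents:** responding share of PBMCs f = 0.10 to 0.30; the same baseline fraction b in all cell types; a moderate change d = 0.20 (20 points) inside responding cells.

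**Step 1: all cells change.**
- Ratio scale: a gain needs 2b < 1, so it is impossible above b = 0.5. A loss needs a fall below b/2: from 0.80 to under 0.40, or from 0.90 to under 0.45. At b = 0.02, any rise above 0.04 is enough.
- M-value scale, where two-fold means doubling or halving the odds b/(1-b): the new fraction is 2b/(1+b) or b/(2-b). From 0.50 that is 0.667 or 0.333; from 0.80, 0.889 or 0.667. Every probe can meet both halves.

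**Step 2: a 20-point change in responding cells only.** The bulk fraction moves by f × d.
- Ratio gain: (b + fd)/b > 2, so b < fd.
- Ratio loss: 1 - fd/b < 0.5 needs b < 2fd. A 20-point loss needs b ≥ d, so f must exceed 0.5. It is never met here.
- M-value gain, with s = fd: b² - (1-s)b + s ≥ 0, so b ≤ [(1-s) - √((1-s)² - 4s)]/2. The upper root lies above 0.80, where a 20-point gain is impossible. For losses the same limit applies to 1-b.

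| f | bulk change | ratio gain needs b below | M-value gain needs b up to | M-value loss needs b from |
|---|---|---|---|---|
| 0.10 | 0.02 | 0.02 | 0.021 | 0.979 |
| 0.20 | 0.04 | 0.04 | 0.044 | 0.956 |
| 0.30 | 0.06 | 0.06 | 0.069 | 0.931 |

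**Step 3: a complete switch in responding cells only.**
- Ratio gain: b + f(1-b) > 2b, so b < f/(1+f) = 0.091, 0.167, 0.231 for f = 0.10, 0.20, 0.30.
- Ratio loss: the bulk fold is 1-f = 0.90, 0.80, 0.70, so 0.5 is not reached unless f exceeds 0.5.
- M-value gain: b ≤ f/(1-f) = 0.111, 0.250, 0.429. M-value loss: b ≥ 1 - f/(1-f) = 0.889, 0.750, 0.571. At f = 0.25 a full switch passes everywhere outside 0.33-0.67.

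**Step 4: how many probes this touches.** The documents give no distribution of baseline methylation. As illustration, three mixtures of Beta(2,30), Beta(3,3) and Beta(20,4) were simulated, with weights 30/20/50, 40/20/40 and 30/10/60; they put 50-65% of probes at or above 0.5. For f = 0.10 to 0.30:
- 20-point change: 4-23% of probes could pass on the ratio scale, 4-29% on M-values.
- Complete switch: 24-42% on the ratio scale, 39-97% on M-values.

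**Step 5: unequal baselines.** Take a mark at 0.90 in responding cells and 0.05 elsewhere that falls to 0.10 in the responding cells. At f = 0.10 the bulk goes from 0.10×0.90 + 0.90×0.05 = 0.135 to 0.10×0.10 + 0.90×0.05 = 0.055, a fold of 0.41. At f = 0.20 and 0.30 it is 0.27 and 0.21. All pass.

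**Step 6: the p-value half.** If no probe differed, 850,000 × 0.05 = 42,500 would have p < 0.05 by chance before any fold filter. The multiple-comparison adjustment mentioned in 10.i belongs to the gene-set analysis, not to the probe calls.

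**The case against.** The strongest reply is that the cell-type question has its own step. Deconvolution is planned for CD4, CD14, CD8, NK and B cells, with checks in purified cells; ATAC-seq is run on cells identified after EDEC, and Section 10.h adds site-specific PCR. Nothing restricts deconvolution to probes that passed the bulk rule. This stands. A reader might infer that true differential methylation will be discarded, or that a null methylation result would reflect only the cut-off. The documents do not support either, because the cell-type route may use every probe.

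A reader might also infer that most probes cannot meet the rule at all. That too fails. The impossibility concerns only the upper half of the rule, on the ratio scale, above 0.5. The lower half is arithmetically open to any probe with some methylation, and on M-values every probe can meet both halves. The plan does not rule out M-values.

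The dilution limits depend on assumptions. Steps 3 and 5 show that full switches on M-values, and marks specific to the responding cells, often pass. The responding share may also be larger than monocytes alone, since Section 1 names NK cells and Section 11 also describes Th1 activation. A larger share widens the window but does not remove the problem for moderate changes: at f = 0.40 a 20-point gain still needs b below 0.08 (ratio) or up to 0.097 (M-values).

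**Conclusion.** The concern holds in a limited form. The scale of the fold is unstated. On the ratio reading, the rule is lopsided by arithmetic alone and blocks hyper-methylation calls above 0.5, the kind of mark that Section 10.j sets out to examine. On both readings it would miss most moderate changes confined to a minority of cells. The size of that loss rests on the assumed 10-30% share, equal baselines and the 20-point change, and the percentages of probes rest on the assumed mixtures as well.

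The loss is certain only for the bulk limma list and the pathway analysis built on it. Whether it carries into deconvolution cannot be settled from the text. The work is a secondary mechanistic analysis on optional blood samples stored for later study. It does not touch the primary endpoint, so the priority is low.

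**What to change.** In Section 10.i:

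- Remove the fold filter for methylation. Test all probes on M-values in limma, with false-discovery-rate control across the roughly 850,000 probes in place of unadjusted p < 0.05.
- Report the absolute methylation difference as the effect size. Pre-specify any minimum difference and justify it against the expected cell share. A fixed 0.05 in bulk would itself miss a 20-point change at a 10% share (0.10 × 0.20 = 0.02); at that share it needs a 50-point change (0.05/0.10).
- State that EDEC and MeDeCom use probes not pre-selected by the bulk rule, and give a criterion for calling a cell-type difference.
- Keep the fold cut-off for ATAC-seq only.

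The cost is a few lines of text, with no new samples or assays, and the change can be made before the stored cells are analysed. The downside is that the probe list then depends on the false-discovery-rate step rather than on effect size, so small but consistent differences may be listed.

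### The methylation pathway analysis names a hypergeometric test with no adjustment for probes per gene, so gene sets rich in probes can be called enriched by chance

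*Combined protocol and SAP*

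**What the plan says.** Section 10.i sets out the methylation analysis in three steps.

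- **Array.** "The Illumina Infinium MethylEPIC array tests ~850,000 methylation sites including promoters, enhancers and non-island sites".
- **Probe selection.** The "limma package will identify probes with greater than 2 or less than 0.5-fold differential methylation with p-values < 0.05". No correction across probes is stated at this step.
- **Gene sets.** GO and gene-set enrichment are run against MSigDB "using hyper-geometric distribution that accounts for multiple comparisons".

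The section gives no rule for turning selected probes into a gene list, no background set of genes, and no weighting by probes per gene. No other section supplies them.

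On standing, section 10.i says "these additional epigenetic studies will be evaluated as part of secondary analysis". Section 10.h describes the mechanism of innate training as a secondary objective. Under section 10.g the blood donation is optional and the cells are stored for later work.

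**The concern.** Selection is made per probe, but the test is made per gene set. The ordinary hypergeometric test treats the gene list as a draw in which every gene has the same chance of appearing. If a gene enters the list when any of its probes is selected, a gene with many probes has more chances to enter than a gene with few. A set made up of probe-rich genes can then look enriched with no methylation difference between the arms. A set of probe-poor genes is penalised in the same way and becomes harder to detect.

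Adjusting for multiple comparisons acts on the p-values after they are computed. Here the null distribution behind each p-value is already wrong, so adjustment raises the bar without correcting the bias. What is at stake is which pathways are reported as reprogrammed by BCG.

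**Working it through.** The plan gives no error rate or power for the enrichment step, so there is no figure of its own to reproduce. The check asks whether, and by how much, the test departs from its nominal error when nothing is differential.

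**Inputs from section 10.i:** about 850,000 sites; selection per probe by fold change and p < 0.05; hypergeometric enrichment with a multiplicity adjustment.

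**Assumed inputs:** 20,000 genes; a gene is listed if at least one of its probes is selected; probes are independent; probe counts are skewed across genes; no true effect. The mean is then 850,000 / 20,000 = 42.5 probes per gene.

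**Chance-call rate a.** Under no effect, p < 0.05 alone gives 850,000 × 0.05 = 42,500 chance calls, so a = 0.05. The two-fold filter lowers a by an unknown amount, so a is varied.

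**Step 1: chance that a null gene is listed.** For m probes, P = 1 − (1 − a)^m.

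| Probes m | a = 0.05 | a = 0.01 | a = 0.001 |
|---|---|---|---|
| 5 | 22.6% | 4.9% | 0.5% |
| 20 | 64.2% | 18.2% | 2.0% |
| 100 | 99.4% | 63.4% | 9.5% |

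Equal probability fails wherever probe counts differ.

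**Step 2: null simulation, all sets in a run equally probe-rich.** Gamma-Poisson probe counts with mean 42.5, sets of 100 genes, upper-tail hypergeometric test. Each cell gives the share of null sets with p < 0.05, then the share significant after Benjamini-Hochberg at 5%.

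| Set's mean probes relative to background | a = 0.05 | a = 0.01 | a = 0.001 |
|---|---|---|---|
| 1.0 | 4.8% / 0% | 3.4% / 0.1% | 2.1% / 0% |
| 1.25 | 48% / 30% | 36% / 8% | 10% / 0.2% |
| 1.5 | 94% / 93% | 74% / 71% | 18% / 1.6% |
| 2.0 | 100% / 100% | 99% / 99% | 50% / 38% |

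**Step 3: a separate null simulation, also with 20,000 genes and skewed counts.** After Benjamini-Hochberg:

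- Sets with twice the average probes: about 5-23% significant at chance-call rates of 0.05-0.1%, and 92-99% at 0.5% or more.
- Sets about 30% richer: about 0-25%.
- Sets of average probe count: about 3-5% before adjustment, so their error rate holds.

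The adjusted figures depend on how many sets in the collection are probe-rich, because the Benjamini-Hochberg threshold loosens as more tests give small p-values. With only 5% of 1,000 sets probe-rich, the two-fold sets give 3% and 13% at rates of 0.05% and 0.1%, and 86-98% at 0.5% or more. The sets about 30% richer give 0.06-6% over rates of 0.05-1%.

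**Step 4: isolating the cause.** With equal probes per gene, the plain test rejects 4.2% at a = 0.01, which is close to nominal. With unequal counts and a non-central hypergeometric test (Fisher form, odds set from probe counts), 1.2-3.3% of null sets have p < 0.05 in every scenario of step 2. At most 0.1% remain after Benjamini-Hochberg.

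**The case against.** The strongest reply is that the defect is partly inferred from silence. The section gives no mapping rule and no software function, and a non-central hypergeometric test belongs to the same family as the one named. **This stands as a limit:** the plan does not exclude a weighted test. But the only adjustment it names is for multiple comparisons, so a reader following the text would run the ordinary test.

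Second, error rates quoted before adjustment exaggerate the problem, because the plan does announce an adjustment. **This stands.** At a = 0.001 and 1.5 times the probes, 18% falls to 1.6%. The size should be judged on adjusted figures.

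Third, stricter probe selection shrinks the bias. **This also stands.** With no true effect at all, false discovery rate control at probe level would usually leave no gene list to bias. The simulations do not test lists that contain true signal.

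Fourth, apart from the array size and the stated selection and test rules, every input is assumed. Spreading all 850,000 sites over genes may overstate the mean, since the array also covers enhancers and non-island sites. Nothing in the documents shows that the immune pathways of interest are probe-rich.

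Two stronger readings are tempting, and the documents do not support either. One is that the whole mechanism claim rests on this test. Sections 10.h to 10.j also plan site-specific PCR, RNA-seq, flow cytometry, ATAC-seq and validation in purified cells. Those steps do not correct a pathway p-value, but they are separate evidence. The other is that multiplicity is ignored at the gene-set step. The plan says there that it is accounted for.

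**Conclusion.** The point holds with limits. As written, the enrichment step is biased toward probe-rich gene sets if one selected probe lists a gene, and the stated multiplicity adjustment lessens the bias without removing it. After adjustment the size runs from negligible (sets modestly richer in probes, few chance calls) to over 90% of null sets (twice the probes, 0.5% or more of probes called by chance). Sets with average probe counts keep their error rate. The loss of power for probe-poor sets follows from the same argument but was not simulated.

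These figures rest on the assumed gene number, probe distribution, independence between probes, mapping rule and absence of true effect. A reader should not infer that every enriched pathway would be false, or that the trial's main results are in doubt. The infection endpoint, the severity endpoint and the sample size do not use this analysis. It is a cheap improvement to a secondary mechanistic analysis.

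**What to change.** In section 10.i:

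1. Replace the hypergeometric test with an enrichment test weighted by the number of probes per gene, for example one based on the Wallenius non-central hypergeometric distribution. If such a test is already intended, say so.
2. Define the background as the genes covered by array probes that pass quality control.
3. State the rule that assigns probes to genes.
4. Keep false discovery rate control across gene sets, and name the method.

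The cost is a little extra specification and analysis work. No new samples and no change to trial conduct are needed, and because the cells are stored for later study the change can be made before the analysis is run.

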12. REGULATORY REQUIREMENTS/REPORTING, MONITORING AND PUBLICATION

a. Financial Disclosure

No financial disclosures to be made. No other commercial support is expended to conduct this study. Merck manufactures the investigational product used in this study and it (or the placebo) will be provided for free to subjects participating in this investigation.

b. IRB Approval

Prior to initiating the study, the investigators will obtain written IRB approval to conduct the study. Should changes to the study protocol become necessary, protocol amendments will be submitted in writing to the IRB by the investigator for IRB approval prior to implementation. Annual progress reports will be submitted to the IRB annually.

c. Ethical conduct of the study

The Investigator agrees, to adhere to the instructions and procedures described in the protocol and conduct the study in accordance with the Code of Federal Regulations (21 CFR Parts 11, 50, 54, 56, 312, 314, and 320), which originate from the ethical principles laid down in the current revision of the Declaration of Helsinki, GCP, and policies and procedures as outlined by the ethical requirements for IRB review and informed consent forms.

d. Ethics and regulatory review

A copy of the protocol, proposed informed consent form, other written subject information, and any proposed advertising material must be submitted to the IRB for written approval. The investigator will notify the IRB of deviations from the protocol or serious adverse events/unanticipated problems occurring in accordance with local procedures.

The investigator is responsible for obtaining annual IRB approval /renewal throughout the duration of the study. The IRB will be notified of completion or termination of this study and sent a copy of the study synopsis in accordance with applicable timelines.

e. Informed consent

The investigator, sub-investigators, and/or designated staff will explain all aspects of the study in lay language and answer all of the subject's questions regarding the study. If the subject desires to participate in the study, s/he will be asked to sign the Informed Consent. No study procedure will be performed prior to signing Informed Consent. All study subjects will be given a copy of the signed Informed Consent(s). Prior to performing any study-related activities under this protocol, written informed consent with the approved ICF must be obtained from the subject or subject's legally authorized representative, as applicable, in accordance with local practice and regulations. The background of the proposed study, procedures, benefits and risks and voluntariness of this study will be explained to the subject.. Full confidentiality of subjects and subject records will be provided according to institutional guidelines. All study subjects will be given a copy of the Informed Consent(s) and given sufficient time to consider whether to participate in the study. The signed consent form will be retained with the study records.

As this study recruits employees, the ICF will also clearly state that involvement is voluntary and not include any coercive language. It will clearly be stated that there will be no favoritism, consternation, retribution or compelling socioeconomic benefits with the participation or refusal to participate in this study.

f. Incentives and Research Related Injury

Patients will not be compensated for participating in this study. Participants will not be charged for the cost of the vaccination (or placebo). If a subject are injured, necessary facilities, emergency treatment and professional services will be available to them, just as they are to the general community.

In the event of injury resulting from this research, or negligence of local study personnel, the study team nor their institution are able to offer financial compensation nor to absorb the costs of medical treatment.

Procedures and treatment for clinical care related to potential adverse events will be billed to the subject and/or their insurance or applicable third party.

g. Changes to the Protocol and/or Informed Consent

Changes to the research covered by this protocol must be implemented by formal protocol amendment. Protocol amendments must not be implemented without prior IRB approval. When the change(s) involve only logistic or administrative aspects of the study, the IRB only

needs to be notified. The data recorded on the CRF and source documents will reflect any departure from the protocol and the source documents will describe the departure and the circumstances requiring it.

A 'substantial amendment' is defined as an amendment to the terms of the IRB application, or to the protocol or any other supporting documentation, that is likely to affect to a significant degree:

- the safety or physical or mental integrity of the subjects of the trial;
- the scientific value of the trial;
- the conduct or management of the trial; or
- the quality or safety of any intervention used in the trial.

h. Annual progress report

The sponsor-investigator will submit a summary of the progress of the trial to their IRB once a year. Information will be provided on the date of inclusion of the first subject, numbers of subjects included and numbers of subjects that have completed the trial, serious adverse events/ serious adverse reactions, other problems, and amendments.

i. Training of site study personnel

The Investigator will assure research activities, including those study-related duties delegated and will be performed by appropriately qualified individuals. The Investigator will assure that study staff will demonstrate due diligence in recruiting and screening study subjects.

The investigator will maintain a list of appropriately qualified persons to whom he/she has delegated study duties. All persons authorized to make entries and/or corrections on case report forms will be included on the Delegation of Authority Form. The investigator and study staff will be responsible for maintaining a comprehensive and centralized filing system of all study-related (essential) documentation, suitable for inspection at any time by applicable regulatory authorities, including completed case report forms, subject identification list, study files and all correspondence to and from the IRBs.

j. Study Management

Each site Investigator will assure proper implementation and conduct of the study will be performed according to the currently approved study protocol.

k. Data Management, Handling, Storage and Security of data and documents

Data will be handled confidentially. A subject identification code list based will be used to link the data to the subject. The key to the code will be safeguarded by each site in a designated location. The electronic CRF (eCRF) are completed on an ongoing basis during the study. The eCRF will be managed via a secure and confidential system (RedCap).

The site principal investigator is responsible for maintaining accurate, complete and up-to-date records for each subject. The site principal investigator is also responsible for maintaining any source documentation.

The investigator is responsible for complying with the requirements for all assessments and data collection as stipulated in the protocol for each subject in the study. For subjects who withdraw prior to completion of all protocol-required data collection and are unable or unwilling to complete, the investigator or study staff can search publically available records [where permitted] to ascertain survival status. This ensures that the data set(s) produced as an outcome of the study is/are as comprehensive as possible.

The investigator and master file and the electronic data from the eCRF will be stored for a duration of 7 years. All information, data, and results that originate from this study may not be disclosed without the written permission of the principal investigator.

I. Temporary halt and end of study report

The sponsor will notify the IRB immediately of a temporary halt of the study, including the reason of such an action. In case the study is ended prematurely, the sponsor will notify the IRB within 15 days, including the reasons for the premature termination. Within one year after the end of the study, the investigator/sponsor will submit a final study report with the results of the study, including any publications/abstracts of the study, to the the IRB. The sponsor will notify the IRB of the end of the study within a period of 90 days. The end of the study is defined as the last patient's last entry into the application. The sponsor will notify the IRB immediately of a temporary halt of the study, including the reason of such an action. In case the study is ended prematurely, the sponsor will notify the IRB and the competent authority within 15 days, including the reasons for the premature termination. Within one year after the end of the study, the investigator/sponsor will submit a final study report with the results of the study, including any publications/abstracts of the study, to the IRB.

m. Monitoring and Quality Assurance

We classify this trial as a low risk study, with a negligible risk because the vaccine is already FDA-approved, and has been shown to be safe in over 3 billion previously administered doses. It has a good safety profile.

n. Audits and Inspections

The Investigator will assure that study staff cooperate with monitoring and audits. The Investigator agrees to allow auditing of all essential clinical study documents by the FDA or other appropriate regulatory authorities. Auditing visits will be scheduled with the appropriate staff at mutually agreeable times as applicable.

o. Confidentiality and Reporting of Results

To maintain subject confidentiality, all data submitted for the current study will be coded using numeric identifiers only. Only on-site research staff will have access to records that may identify subjects. Any paper research and clinical records will be stored on site in a locked cabinet in a secure location. Electronic records will be accessible only by data management staff, clinical monitors and active site personnel who have furnished the required training and credentials. Subject information will not be released without written permission, except as necessary for monitoring by the FDA.

